5.6.3 Laboratory Values

Laboratory results will be summarized using Système International (SI) units. For quantitative parameters listed in [protocol Section 9.5.1.5.3](#), the actual value and the change from baseline to each postbaseline visit will be summarized by visit and treatment group using descriptive statistics. Qualitative parameters listed in protocol Section 9.5.1.5.3 will be summarized using frequencies (number and percentage of subjects), and changes from baseline to each postbaseline visit and to end of treatment will be reported using shift tables. Percentages will be based on the number of subjects with both nonmissing baseline and relevant postbaseline results.

Laboratory test results will be assigned a low/normal/high (LNH) classification according to whether the value was below (L), within (N), or above (H) the laboratory parameter's reference

range. Within-treatment comparisons for each laboratory parameter will be based on 3-by-3 tables (shift tables) that compare the baseline LNH classification to the LNH classification at each postbaseline visit and at the end of treatment. Similar shift tables will be used to compare the baseline LNH classification to the LNH classification for the highest and lowest value during the study.

The Sponsor's Grading for Laboratory Values using CTCAE v4.0 presents the criteria that will be used to identify subjects with treatment-emergent markedly abnormal laboratory values (TEMAVs). Except for phosphate, a TEMA is defined as a postbaseline value with an increase from baseline to a grade of 2 or higher. For phosphate, a TEMA is defined as a postbaseline value with an increase from baseline to a grade of 3 or higher. When displaying the incidence of TEMAVs, each subject will be counted once in the laboratory parameter high and in the laboratory parameter low categories, as applicable.

Laboratory results versus visit by treatment group will be displayed using box-plot.

Subject data listings of Laboratory test results and TEMA will be provided.

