9.5.1.3.5 ASSESSMENT OF C-REACTIVE PROTEIN (CRP)

CRP of each subject will be measured as part of blood biochemical tests during the Screening Phase, Observation Phase, Treatment Phase (Weeks 2, 4, 8, 12, 16, 20, and 24), Extension Phase (every 4 weeks up to Week 104), and at discontinuation.

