9.7.1.8.3 LABORATORY VALUES

Laboratory results will be summarized using Système International (SI) units. For continuous variables, summary statistics for the actual value and the change from baseline will be summarized by visit.

For ordinal classification parameters, laboratory test results will be assigned a low/normal/high (LNH) classification according to whether the value was below (L), within (N), or above (H) the laboratory parameter's reference range. The number (percentage) of subjects by LNH will be summarized on shift tables (the baseline vs. each postbaseline visit) by treatment group. Similar shift tables will also compare the baseline LNH classification to the LNH classification for the highest and lowest value after starting the study drug administration.

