9.7.1.9 Extension Phase Analyses

Similar analyses to those described in the above sections for the Treatment Phase will be conducted for efficacy, pharmacokinetics (except for population PK and PK/PD analyses), biomarker, immunogenicity, and safety endpoints by treatment group of the Treatment Phase.

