8 DEFINITIONS AND CONVENTIONS FOR DATA HANDLING

8.1 Baseline, Time Windows for statistical analyses

8.1.1 Definition of baseline value

The baseline value was defined as the most recent value reported just before first dosing.

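### SAP 5.6.3 draws the highest/lowest-value laboratory shift tables from the whole study, while the protocol uses post-dose values only; the effect is small, undeclared and fixed by one phrase

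*SAP*

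**What the plan says.** For the extreme-value laboratory shift tables, Protocol 9.7.1.8.3 compares baseline with the "LNH classification for the highest and lowest value after starting the study drug administration". Protocol 9.7.1.9 carries the approach into the Extension Phase: "Similar analyses to those described in the above sections for the Treatment Phase will be conducted".

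SAP 5.6.3, which covers the Extension Phase, instead plans tables that "compare the baseline LNH classification to the LNH classification for the highest and lowest value during the study". It states no lower time limit. The sentence just before it, on the other shift tables, is explicitly post-dose: those tables "compare the baseline LNH classification to the LNH classification at each postbaseline visit and at the end of treatment". The definition of treatment-emergent markedly abnormal values (TEMAVs) in the same section also refers to postbaseline values.

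SAP 8.1.1 fixes baseline: "The baseline value was defined as the most recent value reported just before first dosing". SAP section 7 lists two departures from the protocol (efficacy summarized to Week 84, PK as a listing only). The laboratory rule is not among them.

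**The concern.** The study begins before the first dose, so the SAP wording admits two kinds of value that the protocol wording keeps out.

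- **The Screening value.** Where a test is drawn at both Screening and Observation, baseline is the Observation value and Screening is a separate pre-dose record. An abnormality seen only at Screening could then appear as a change under E6011.
- **The baseline value itself.** A maximum that includes baseline cannot fall below baseline, and a minimum cannot rise above it. Some improvement cells are then empty whatever the data show.

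Safety and tolerability form a primary objective. Everyone in the Extension Phase receives open-label E6011, so there is no concurrent control against which a spurious shift could be judged.

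**Working it through.** The plan states no figure on this point, so the check is of the definition first and of its likely size second.

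**1. Which tests have a separate Screening record (Protocol Table 4)**

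| Tests | Screening | Observation | Screening route possible? |
|---|---|---|---|
| Hematology, chemistry, urinalysis | yes | yes | yes |
| KL-6, β-D glucan | yes | no | no: Screening is the only scheduled pre-dose sample |
| Autoantibodies, vasculitis markers | no | yes | no: Observation is the only pre-dose sample |

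Protocol 9.5.1.3.5 confirms the first row for one chemistry test: "CRP of each subject will be measured as part of blood biochemical tests during the Screening Phase, Observation Phase, Treatment Phase".

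**2. Which cells can be reached**

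Order the classes L < N < H. The highest-value table plots baseline against the maximum of the pool, and the lowest-value table plots it against the minimum.

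- *Post-dose pool (protocol).* Baseline puts no limit on the maximum or minimum, so all 9 cells are reachable in both tables.
- *Whole-study pool (SAP, literal).* The maximum is at least baseline, so the highest-value table loses H→N, H→L and N→L. The minimum is at most baseline, so the lowest-value table loses L→N, L→H and N→H.
- Adding baseline alone to the post-dose pool already removes exactly these cells. Adding Screening removes no more. The empty cells therefore come from baseline, and the false shifts come from Screening.
- L→N stays reachable in the highest-value table and H→N in the lowest-value table.

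*Example.* Screening H, baseline N, all post-dose N: the protocol rule gives N→N and the SAP rule gives N→H in the highest-value table.

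**3. Illustrative size**

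Assumptions, none of them from the documents: no drug effect; standard normal values; reference range equal to the central 95% (limits ±1.96); within-subject correlation ρ from 0.5 to 0.85.

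Number of post-dose samples n: Protocol Table 5 schedules 7 + 20 = 27 through Week 104. A subject followed to Week 76 has 7 + (76 − 24)/4 = 7 + 13 = 20.

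Given subject effect u ~ N(0, 1), one sample is high with probability p = 1 − Φ((1.96 − √ρ·u)/√(1 − ρ)) and low with probability q = Φ((−1.96 − √ρ·u)/√(1 − ρ)). Averaging over u:

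- False N→H among baseline-normal subjects (high at Screening, never high post-dose) = E[(1 − p − q)·p·(1 − p)ⁿ] / E[1 − p − q].
- H→N that the highest-value table would lose, among baseline-high subjects = E[p·(1 − p)ⁿ] / E[p].

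| ρ | n | N→H, post-dose pool | N→H, Screening added | False N→H (percentage points) | H→N lost, of baseline-high |
|---|---|---|---|---|---|
| 0.5 | 20 | 20.1% | 20.6% | 0.52 | 20.7% |
| 0.5 | 27 | 23.4% | 23.8% | 0.42 | 16.4% |
| 0.85 | 20 | 7.5% | 7.7% | 0.14 | 5.7% |
| 0.85 | 27 | 8.4% | 8.6% | 0.11 | 4.4% |

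Differences were taken before rounding. By symmetry the same figures hold for N→L and L→N in the lowest-value table. Take 50 baseline-normal subjects, the planned size of the larger arms. The false entries expected per parameter and direction are then 50 × 0.0011 ≈ 0.06 to 50 × 0.0052 ≈ 0.26 of a subject.

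**The case against.** The best defence is that the SAP authors meant post-dose values all along. The sentence opens by calling these tables similar to ones that are explicitly postbaseline. Shortly before, the section says: "Percentages will be based on the number of subjects with both nonmissing baseline and relevant postbaseline results". The laboratory windows in SAP Table 8.3 start at Week 2 and define no Screening window. Silence in section 7 fits no intended change at least as well as an undeclared one.

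This stands as evidence of intent, and a reader should not infer that the SAP deliberately adopted a new rule. It does not settle the rule. The percentages sentence follows the text on qualitative parameters and decides who is counted, not which values enter a maximum or minimum. The windows assign records to visits, and an extreme over a period is not a visit. Two programmers could properly produce different tables.

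The defence is also right on importance. The tables are descriptive, with no test or decision attached. TEMAVs, which capture marked abnormalities, are defined on postbaseline values. Visit summaries and box-plots are by visit.

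A reader might infer that the entry rules make pre-dose abnormalities common, since AST or ALT up to 3 × ULN is admitted and inclusion criterion 6 uses CRP. The documents do not support this. Admitting a value does not make it frequent, criterion 6 can be met by ESR alone, and a false CRP shift also needs a normal CRP at Observation and at every post-dose visit. The documents give neither reference ranges nor abnormality rates.

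**Conclusion.** The point holds as a conflict of wording that gives wrong cells if the SAP is followed to the letter. It is minor.

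- For hematology, chemistry and urinalysis, a Screening-only abnormality can be tabulated as a shift from normal.
- Baseline-High subjects cannot show High-to-Normal in the highest-value table, nor baseline-Low subjects Low-to-Normal in the lowest-value table.

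A reader might go further and conclude that return to normal can never be seen. It can: in the by-visit and end-of-treatment tables, and in the opposite-extreme table, where those cells remain open.

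Under the stated assumptions, false shifts amount to about 0.1 to 0.5 percentage points per parameter and direction, against N→H rates of about 8% to 20% or more from post-dose values alone. Larger figures arise only with far fewer samples, for example 8 per subject. That is a subject who leaves after about one Extension Phase sample and is not representative of 27 scheduled draws. The logic of the empty cells needs no assumptions; the percentages rest on them entirely.

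**What to change.** In SAP 5.6.3, end the sentence on the extreme-value tables with *for the highest and lowest postbaseline value (after the first dose of study drug)*. This matches Protocol 9.7.1.8.3, makes all nine cells reachable in both tables, and stops a Screening value from creating a shift. If the whole-study pool was intended, list it in SAP section 7 with a reason.

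The cost is one phrase and a date filter in the program. No new data are needed.

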23. Tested positive for any of the following in the Screening Phase: HIV, hepatitis B virus surface antigen (HBs antigen), hepatitis B virus surface antibody (HBs antibody), hepatitis B virus core antibody (HBc antibody), hepatitis B virus DNA (HBV DNA), hepatitis C virus antibody (HCV antibody), human T-lymphotrophic virus type I antibody (HTLV-1 antibody), or syphilis (except if positive for the HBs antibody only, and it is clear that this is due to hepatitis B vaccination. In case of positive RPR and negative TP antibody results in the syphilis test, the positive result is not considered valid if a false positivity is confirmed by repeated TP antibody negative results of other syphilis tests performed 21 days or more later). For subjects who are negative for both HBs antigen and HBV-DNA quantitative test and positive for either or both of anti-HBc antibody and anti-HBs antibody, their study participation is allowed if the investigator or subinvestigator takes a proper measure such as HBV-DNA monitoring based on the "Guideline for measures against hepatitis B caused by immunosuppression and chemotherapy."
24. Positive in tuberculosis test (QuantiFERON[®]TB Gold Test or T-SPOT[®].TB Test) in the Screening Phase. For those whose results are "hold" (indeterminable) in repeated tests, their study participation is only allowed if they start receiving a prophylactic treatment with isoniazid (in principle, 300 mg/day [5 mg/kg/day in case of low weight] for approximately 9 months) \geq 21 days before starting the study treatment.
25. Findings indicating a history of tuberculosis on chest x-ray in the Screening Phase
26. Neurological findings such as motor paralysis, visual impairment, or language disorder in the Screening Phase
27. Blood CD4-positive cell count <200 / μ L or white blood cell count $<3,000$ / μ L in the Screening Phase
28. Any of the following laboratory abnormalities in the Screening Phase
 - Hemoglobin: <8.0 g/dL

- Neutrophil count: <1,500 / μ L
- Platelet: <100,000 / μ L
- AST or ALT: >3 \times the upper limit of normal (ULN)
- Serum creatinine: >1.5 mg/dL
- Serum KL-6: >ULN
- β -D glucan: >ULN

29. Demonstrated prolonged QTcF interval (>450 ms) in repeated ECG examinations

30. Women of childbearing potential who have a positive pregnancy test in the Screening or Observation Phase or of breastfeeding

31. Women of childbearing potential who:

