13 APPENDICES

13.1 National Institute for Health: Common Terminology Criteria for Adverse Events (CTCAE) Version 4.0

National Cancer Institute (NCI) CTCAE version 4.0 May 2009 is available online at:

https://evs.nci.nih.gov/ftp1/CTCAE/Archive/CTCAE_4.0_2009-05-29_QuickReference_5x7.pdf

CTCAE grades for selected laboratory parameters are listed in the table below, where ULN is the upper limit of normal and LLN is the lower limit of normal.

Lab Parameter	NCI Common Terminology Criteria for Adverse Events (CTCAE) - SI Units				
	Grade 1	Grade 2	Grade 3	Grade 4	Grade 5
Hematology					
Hemoglobin (low)	< LLN - 100 (g/L)	< 100 - 80 (g/L)	< 80 - 65 (g/L)		Death
Hemoglobin (high)	Increase in > 0 - 20 (g/L) above ULN or above baseline if baseline is above ULN	Increase in >20 - 40 (g/L) above ULN or above baseline if baseline is above ULN	Increase in > 40 (g/L) above ULN or above baseline if baseline is above ULN		
Platelet Count (PLT) (low)	< LLN - 75.0 ($10^9/L$)	< 75.0 - 50.0 ($10^9/L$)	< 50.0 - 25.0 ($10^9/L$)	< 25.0 ($10^9/L$)	
White Blood Cell Count (WBC) (low)	< LLN - 3.0 ($10^9/L$)	< 3.0 - 2.0 ($10^9/L$)	< 2.0 - 1.0 ($10^9/L$)	< 1.0 ($10^9/L$)	
White Blood Cell Count (WBC) (high)			> 100 ($10^9/L$)		Death
Lymphocytes (low)	< LLN - 0.8 ($10^9/L$)	< 0.8 - 0.5 ($10^9/L$)	< 0.5 - 0.2 ($10^9/L$)	< 0.2 ($10^9/L$)	
Lymphocytes (high)		> 4 - 20 ($10^9/L$)	> 20 ($10^9/L$)		
Neutrophils (low)	< LLN - 1.5 ($10^9/L$)	< 1.5 - 1 ($10^9/L$)	< 1 - 0.5 ($10^9/L$)	< 0.5 ($10^9/L$)	
Blood Chemistry					
Albumin (low)	< LLN - 3 (g/dL) ; < LLN - 30 (g/L)	< 3 - 2 (g/dL) ; < 30 - 20 (g/L)	< LLN - 2 (g/dL) ; < 20 (g/L)		Death
Alkaline Phosphatase (high)	> ULN - 3.0 x ULN	> 3.0 - 5.0 x ULN	> 5.0 - 20.0 x ULN	> 20.0 x ULN	
Alanine Aminotransferase (high)	> ULN - 3.0 x ULN	> 3.0 - 5.0 x ULN	> 5.0 - 20.0 x ULN	> 20.0 x ULN	
Amylase (high)	> ULN - 1.5 x ULN	> 1.5 - 2.0 x ULN	> 2.0 - 5.0 x ULN	> 5.0 x ULN	

Lab Parameter	NCI Common Terminology Criteria for Adverse Events (CTCAE) - SI Units				
	Grade 1	Grade 2	Grade 3	Grade 4	Grade 5
Aspartate Aminotransferase (high)	> ULN - 3.0 x ULN	> 3.0 - 5.0 x ULN	> 5.0 - 20.0 x ULN	> 20.0 x ULN	
Total Bilirubin (high)	> ULN - 1.5 x ULN	> 1.5 - 3.0 x ULN	> 3.0 - 10.0 x ULN	> 10.0 x ULN	
Corrected Calcium*, serum-low (hypocalcemia)	< LLN - 2.0 (mmol/L) ; < LLN - 8.0 (mg/dL)	< 2 - 1.75 (mmol/L) ; < 8.0 - 7.0 (mg/dL)	< 1.75 - 1.5 (mmol/L) ; < 7.0 - 6.0 (mg/dL)	< 1.5 (mmol/L) ; < 6.0 (mg/dL)	Death

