13.2 Sponsor's Grading for Determining Markedly Abnormal Laboratory Results

Except for phosphate, a TEMAV is defined as a postbaseline value with an increase from baseline to a grade of 2 or higher. For phosphate, a TEMAV is defined as a postbaseline value with an increase from baseline to a grade of 3 or higher.

SIGNATURE PAGE

Author:

PPD

Date

Approval:

PPD

24 May 2020

Date

PPD

Date

Neurology Business Group

PPD

Date

SIGNATURE PAGE

Author:

PPD

Date

Approval:

PPD

Date

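### A postbaseline hemoglobin below 65 g/L has no grade in the SAP's table, so that value cannot be flagged as markedly abnormal, while a milder 65 to 79 g/L can

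*SAP*

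**What the plan says.** SAP 5.6.3 refers to a sponsor's laboratory grading based on CTCAE v4.0, which "presents the criteria that will be used to identify subjects with treatment-emergent markedly abnormal laboratory values (TEMAVs"). The rule is that "a TEMA is defined as a postbaseline value with an increase from baseline to a grade of 2 or higher"; phosphate needs Grade 3. (The SAP prints both TEMA and TEMAV for the same term.) SAP 13.2 repeats the rule and adds no limits: "Except for phosphate, a TEMAV is defined as a postbaseline value with an increase from baseline to a grade of 2 or higher". On counting, SAP 5.6.3 says that "each subject will be counted once in the laboratory parameter high and in the laboratory parameter low categories, as applicable".

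The grades are in SAP Appendix 13.1. The low-hemoglobin row prints:

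| Grade | Low hemoglobin, g/L |
|---|---|
| 1 | 100 to below the lower limit of normal (LLN) |
| 2 | 80 to below 100 |
| 3 | 65 to below 80 |
| 4 | empty |
| 5 | death |

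Protocol 9.3.2, exclusion 28, bars "Hemoglobin: <8.0 g/dL" in the Screening Phase, which is 80 g/L. SAP 8.1.1 takes as baseline the last value before first dosing, which need not be the screening value.

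**The concern.** A living subject with hemoglobin below 65 g/L fits no band in the row. With no grade, the value cannot be an increase to Grade 2 or higher, so the flag switches off at the point where the abnormality becomes most severe. The TEMAV table and its listing are where the SAP grades laboratory results by severity. In that output a milder value counts and a worse one does not.

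The low/normal/high shift tables do not fully make up for this. For a subject already below the reference range at baseline, they show low to low whether the later value is 85 or 60 g/L.

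**Working it through.** The plan states no figure to reproduce here. The check applies the printed bands and the TEMAV rule literally.

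**Inputs.** The bands are those of SAP 13.1. The rule is that the postbaseline grade is at least 2 and higher than the baseline grade (SAP 5.6.3). The screening floor is 8.0 g/dL × 10 = 80 g/L (Protocol 9.3.2). The documents give no LLN for hemoglobin. Values from 110 to 137 g/L were assumed, and the result below 65 g/L is the same throughout.

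**Step 1: single values.**

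| Postbaseline, g/L | Grade as printed | TEMAV from baseline 130 | TEMAV from baseline 95 (Grade 2) |
|---|---|---|---|
| 99 | 2 | yes | no |
| 79 | 3 | yes | yes |
| 65 | 3 | yes | yes |
| 64.9 | none | no | no |
| 50 | none | no | no |

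A subject whose baseline is 80 to 99 g/L is already Grade 2, so only the band from 65 to below 80 g/L can flag them. A fall of more than 80 − 65 = 15 g/L (from 80) or 99 − 65 = 34 g/L (from 99) takes the value past that band.

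**Step 2: whole subjects.** Counting is once per subject, so the other visits matter.

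| Postbaseline visits, g/L | Baseline 130 | Baseline 90 |
|---|---|---|
| 125, 60, 112 | not counted | not counted |
| 125, 90, 60, 85 | counted, through 90 and 85 | not counted |
| 75, 60 | counted, through 75 | counted, through 75 |

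All six are counted once values below 65 g/L carry a grade.

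**Step 3: is this a convention of the table?** The worst numeric band was checked in all 30 rows. Several rows have no Grade 4 limit, but their last band is open. High hemoglobin, for example, ends at "Increase in > 40 (g/L) above ULN or above baseline if baseline is above ULN". High white cell count ends above 100, high lymphocytes above 20, and urine protein at 2+ or more. Low albumin ends below 20 g/L; its g/dL entry is printed differently, but SAP 5.6.3 reports in SI units. Low hemoglobin is the only row closed at its worst end.

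**Step 4: size.** The documents give no incidence. As an assumption only, if 0% to 1% of subjects ever fall below 65 g/L, the ceiling is 0 to 0.01 × 175 = 1.75 subjects. The true base is at most 175, because SAP 5.2.1 requires a dose and a safety assessment after Week 24. Those missed from the TEMAV table are a subset of these subjects.

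**The case against.** The strongest reply is that little is lost. SAP 5.6.3 also calls for summary statistics by visit, box plots, a listing of laboratory results, and shift tables for the lowest value during the study. A subject normal at baseline who falls to 60 g/L moves from normal to low there. Under Protocol 9.5.1.5.1, a laboratory abnormality that leads to intervention or to stopping or withholding drug is an adverse event with a CTCAE grade, and SAP 5.6.2 tabulates events by maximum intensity. This stands. A reader might infer that the most severe anemia is never counted or disappears from the safety report. The documents do not support that: the gap concerns a value in one output, and Step 2 shows that a subject can still be counted through another visit.

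A second reply is that SAP 13.1 links to the full CTCAE and SAP 9 leaves derivation rules to separate documents, so the program may treat anything below 80 g/L as at least Grade 3. That is possible and cannot be checked from these documents. It does not change the rule as printed, which says nothing of the kind.

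A third is that the empty cell may be a fault in reading the PDF. That is unlikely. The lower bound of 65 is printed text, and death sits in the Grade 5 position after one empty cell, as in the high white cell row.

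**Conclusion.** The grading rule is wrong as written, in a small way. A postbaseline hemoglobin below 65 g/L has no grade and cannot be a TEMAV, while 65 to 79 g/L can. A subject is missed in the TEMAV table only when no other visit reaches Grade 2 or higher above the baseline grade. The number is likely very small and could be zero. No endpoint, test or decision rule depends on it.

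The conclusion rests on a literal reading of Appendix 13.1 and does not depend on the LLN. It covers the Extension Phase analysis in this SAP. The Treatment Phase SAP required by Protocol 9.7 is not among the documents.

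A reader might also infer that correcting the row makes every value below 65 g/L a TEMAV. That goes too far. The 80 g/L floor applies at screening, but baseline is the last value before dosing. A subject whose baseline is 65 to 79 g/L is already Grade 3, so under an open-ended Grade 3 a later 60 g/L is no increase.

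**What to change.** Either change is enough:

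- in Appendix 13.1, print Grade 3 for low hemoglobin as below 80 g/L, with no lower bound; or
- add to SAP 5.6.3 that a value beyond the last numeric limit takes the highest numeric grade printed for that parameter.

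Any value below 65 g/L is then a TEMAV for subjects whose baseline grade is below 3. For subjects with a baseline of 65 g/L or more, no result at or above 65 g/L changes. The cost is one table cell or one sentence, plus a check that the program matches. No new data are needed.
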